## **8.2. Laboratory Test Abnormalities**

Laboratory abnormalities that constitute an AE in their own right (considered clinically meaningful, induce clinical signs or symptoms, require concomitant therapy, or require changes in study drug) should be recorded on the Adverse Event form in the eCRF. Whenever possible, a diagnosis rather than a symptom should be provided (eg, "anemia" instead of "low hemoglobin"). Laboratory abnormalities that meet the criteria for AEs should be followed until they have returned to normal or an adequate explanation of the abnormality is found. When an abnormal laboratory test result corresponds to a sign or symptom of a previously reported AE, it is not necessary to separately record the laboratory test result as an additional event.

Laboratory abnormalities that do not meet the definition of an AE should not be reported as AEs. A Grade 3 or 4 AE does not automatically indicate an SAE unless it meets the definition of serious, as defined in Section 8.3.1, and/or per the investigator's discretion. A dose modification for the laboratory abnormality may be required (see Section 5.4.2) and should not contribute to the designation of a laboratory test abnormality as an SAE.

## **8.3. Serious Adverse Events**

### **8.3.1. Definitions**

An SAE is defined as an event that meets at least 1 of the following criteria:

- Is fatal or life-threatening.
- Requires inpatient hospitalization or prolongation of existing hospitalization, unless hospitalization is a result of:
  - A routine treatment or monitoring of the studied indication not associated with any deterioration in condition.
  - An elective or preplanned treatment for a pre-existing condition that is unrelated to the indication under study and has not worsened since signing the ICF.
  - A treatment on an emergency outpatient basis for an event not fulfilling any of the definitions of a SAE and not resulting in hospital admission.
  - Any social reasons and respite care, in the absence of any deterioration in the subject's general condition.
- Results in persistent or significant disability, incapacity, or a substantial disruption of a person's ability to conduct normal life functions.
- Constitutes a congenital anomaly or birth defect.

- Is considered to be an important medical event or a medically significant event that may not result in death, be immediately life-threatening, or require hospitalization but may be considered serious when, based upon appropriate medical judgment, the event may jeopardize the subject or may require medical or surgical intervention to prevent 1 of the outcomes listed above.

### **8.3.2. Reporting**

To ensure subject safety, every SAE, regardless of suspected causality (including events that may not be associated with the study drug[s] but may be associated with a study procedure or disease progression), unless otherwise specified by the Protocol, occurring after the subject has signed the ICF and up to the last study visit, or up to 30 days after the subject has stopped study treatment, whichever is later, must be reported to the sponsor (or designee) within **24 hours** of learning of its occurrence. Any SAEs occurring more than 30 days after the last dose of study drug should be reported to the sponsor, or its designee, only if the investigator suspects a causal relationship to the study drug. An SAE occurring at a different time interval or otherwise considered completely unrelated to a previously reported SAE should be reported separately as a new event. Previously planned (ie, before providing informed consent) surgeries should not be reported as SAEs unless the underlying medical condition worsens over the course of the study.

Information about all SAEs is collected and recorded on the Adverse Event form of the eCRF. The investigator must assess and record the causal relationship of each SAE to each specific study drug (itacitinib/placebo and the corticosteroid during the time it is given).

The investigator must also complete the Incyte Serious Adverse Event Report Form, in English, and send the completed and signed form to the sponsor or designee within 24 hours of becoming aware of the SAE. The investigator must provide a causality assessment, that is, assess whether there is at least a reasonable possibility that the SAE is related to the study treatment: suspected (yes) or not suspected (no). Refer to the Incyte Reference Guide for Completing the Serious Adverse Event Report Form.

The contact information of the sponsor's study-specific representatives is listed in the investigator manual provided to each site. The original copy of the SAE Report Form and the confirmation sheet must be kept at the study site.

Investigational site personnel must report any new information regarding the SAE within 24 hours of becoming aware of the information in the same manner that the initial SAE Report Form was sent. Follow-up information is recorded on an amended or new SAE Report Form, with an indication that it is follow-up to the previously reported SAE and the date of the original report. The follow-up report should include information that was not provided on the previous SAE Report Form, such as the outcome of the event (eg, resolved or ongoing), treatment provided, action taken with study drug because of the SAE (eg, dose reduced, interrupted, or discontinued), or subject disposition (eg, continued or withdrew from study participation). Each recurrence, complication, or progression of the original event should be reported as follow-up to that event, regardless of when it occurs.

If the SAE is not documented in the IB for itacitinib (new occurrence) and is thought to be related to the sponsor's study drug, the sponsor or its designee may urgently require further information from the investigator for reporting to health authorities. The sponsor or its designee

may need to issue an Investigator Notification (IN) to inform all investigators involved in any study with the same drug that this SAE has been reported. Suspected Unexpected Serious Adverse Reactions (SUSARs) will be collected and reported to the competent authorities and relevant ethics committees in accordance with Directive 2001/20/EC, or as per national regulatory requirements in participating countries.

#### **8.4. Emergency Unblinding of Treatment Assignment**

The procedure for emergency unblinding is provided in the study reference manual. This option may be used ONLY if the subject's well-being requires the investigator to be aware of the subject's treatment assignment.

The investigator should make every effort to contact the sponsor's medical monitor before unblinding a subject's treatment assignment; however, this is not mandatory. If a subject's treatment assignment is unblinded, the sponsor or its designee must be notified immediately by telephone.

If an investigator, site personnel performing assessments, or subject is unblinded, the subject must be withdrawn from the study treatment. In cases where there are ethical reasons to have the subject remain in the study, the investigator must obtain specific approval from the sponsor's (or its designee's) clinical research physician or medical monitor for the subject to continue in the study.

#### **8.5. Pregnancy**

Pregnancy, in and of itself, is not regarded as an AE unless there is suspicion that study drug may have interfered with the effectiveness of a contraceptive medication or method. When a pregnancy has been confirmed in a subject during maternal or paternal exposure to study drug, the following procedures should be followed in order to ensure subject safety:

- The study drug must be discontinued immediately (female subjects only; see Section 5.4 for the maximum permitted duration of study drug interruption).
- The investigator must complete and submit the Incyte Clinical Trial Pregnancy form to the sponsor or its designee within **24 hours** of learning of the pregnancy.

Data on fetal outcome and breastfeeding are collected for regulatory reporting and drug safety evaluation. Follow-up should be conducted for each pregnancy to determine outcome, including spontaneous or voluntary termination, details of the birth, and the presence or absence of any birth defects, congenital abnormalities, or maternal and/or newborn complications, by following until the first well-baby visit. Pregnancy should be recorded on a Clinical Trial Pregnancy form and reported by the investigator to the sponsor or its designee. Pregnancy follow-up information should be recorded on the same form and should include an assessment of the possible causal relationship to the sponsor's study drug to any pregnancy outcome, as well as follow-up to the first well-baby visit or the duration specified in local regulations, whichever is later. Refer to the Incyte Reference Guide for Completing the Clinical Trial Pregnancy Form.

**Any SAE occurring during pregnancy must be recorded on the SAE report form and submitted to the sponsor or designee.**

## **8.6. Warnings and Precautions**

Special warnings or precautions for the study drug, derived from safety information collected by the sponsor or its designee, are presented in the [IB](#). Additional safety information collected between IB updates will be communicated in the form of Investigator Notifications (INs). Any important new safety information should be discussed with the subject during the study, as necessary. If new significant risks are identified, they will be added to the ICF.

## **8.7. Data Monitoring Committee**

An external DMC will be formed to monitor the study. The DMC will consist of external investigators who will function autonomously from all other individuals associated with the conduct of the trial, including investigators and sponsor personnel. The DMC will be responsible for reviewing results from the prespecified interim analysis and recommending an appropriate course of action based on these data. Details on the composition and responsibilities of the DMC can be found in the DMC charter.

## **8.8. Product Complaints**

The sponsor collects product complaints on study drugs and drug delivery systems used in clinical studies in order to ensure the safety of study participants, monitor quality, and facilitate process and product improvements.

All product complaints associated with material packaged, labeled, and released by the sponsor or its designee will be reported to the sponsor. All product complaints associated with other study material will be reported directly to the respective manufacturer.

The investigator or his/her designee is responsible for reporting a complete description of the product complaint via email or other written communication to the sponsor contact or respective manufacturer as noted in the packaging information. Any AE associated with a product complaint should be reported as described in [Section 8.1.2](#) of this Protocol.

If the investigator is asked to return the product for investigation, he/she will return a copy of the product complaint communication with the product.

## 9. STATISTICS

### 9.1. Study Populations

Subject enrollment, disposition, demographics, and medical history will be summarized at baseline. Dose exposure will be calculated for each dose level. Safety and disease response data will be compared over time to assess change from baseline, during treatment, and follow-up.

The populations to be analyzed include the following:

- Efficacy evaluable population: Subjects randomized into the study.
- Per-Protocol population: A subset of subjects in the efficacy evaluable population who are compliant with requirements of the clinical study Protocol, including:
  - Continued to meet all eligibility criteria on Study Day 1.
  - Initiated correct randomized therapy within the Protocol-specified window.
  - Did not significantly deviate from the Protocol in terms of missed study visits, noncompliance with randomized therapy, or prohibited concomitant medications.
- Safety evaluable population: Subjects randomized into the study who received at least 1 dose of study drug.
- Pharmacokinetic and translational research evaluable population: Subjects who receive at least 1 dose of study drug and provide at least 1 plasma sample (1 corresponding PK or translational research measurement) after study drug administration will be considered as potential PK evaluable subjects. The study pharmacokineticist will review data listings of study drug administration and sample records to identify subjects to be excluded from analyses of PK data.

### 9.2. Selection of Sample Size

A sample size of 414 subjects with 1:1 randomization (itacitinib vs placebo) and stratification based on aGVHD risk status (standard risk vs high risk) provides approximately 90% power to test for the primary endpoint (ORR at Day 28) and 83% power to test for the key secondary endpoint (NRM at Month 6). The family-wise  $\alpha$ -level will be controlled at 0.025 overall for the two comparisons. Specifically, this study will claim to have achieved the efficacy objective when the primary endpoint ORR at Day 28 shows a significant treatment effect at 1-sided  $\alpha = 0.025$ . Conditional on significance of the primary endpoint, the key secondary endpoint (NRM at Month 6) will be tested at 1-sided  $\alpha = 0.025$ .

An absolute improvement of 16% in the primary endpoint of ORR at Day 28 would be considered a clinically meaningful improvement over standard first-line systemic treatment for aGVHD (standard care ORR at Day 28:  $P_0 = 0.56$ ; itacitinib ORR at Day 28:  $P_1 = 0.72$ ). A sample size of 414 subjects (207 subjects per treatment arm) will provide approximately 90% power to detect a 16% overall difference (72% vs 56%) between treatment cohorts for the primary endpoint (ORR at Day 28) at a 1-sided alpha level of 0.025. A CMH test with 2-strata will be used.

The assumed Day 28 ORR of 56% is based on MacMillan et al (2015). The stratum-specific response rates (standard risk, 68%; high risk, 44%) assume a standard risk:high risk ratio of 0.50:0.50. It is expected that treatment with itacitinib will result in a 16% increase in the ORR, that is, an expected odds ratio of 2.02 (which corresponds to an overall increase in ORR to 72%), with stratum-specific response rates of 81% and 61% for standard-risk and high-risk aGVHD cohorts, respectively. Power for the CMH test with stratification based on GVHD risk score was calculated using software N-Query 5.0.

Given its clinical significance, NRM at Month 6 will be assessed as the key secondary endpoint. Based on MacMillan et al (2015), the overall NRM at Month 6 in the BAT arm is 33%, with a stratum-specific NRM of 22% for standard risk and 44% for high risk (assuming a standard risk:high risk ratio of 0.50:0.50). A 40% relative reduction in NRM rate will be considered a clinically meaningful improvement. A sample size of 414 subjects (207 subjects per treatment cohort) will provide 83% power to detect a relative reduction of 40% (or absolute difference of 13.2%, ie, 19.8% vs 33% at Day 180) between treatment cohorts at a 1-sided  $\alpha$  level of 0.025 with an odds ratio of 0.50. A CMH test with 2-strata will be used. Stratum-specific NRM rates of 12.4% and 28.2% are expected for standard-risk and high-risk cohorts, respectively. Power for the CMH test with stratification based on GVHD risk score was calculated using software N-Query 5.0.

In order to compensate for an anticipated early withdrawal rate of up to 5% (ie, subjects who do not have any response data before Day 28), a total of 436 subjects (218 per treatment arm) will be randomized into the study to ensure a sample size of 414 evaluable subjects.

If the Day 180 NRM rate difference between 2 groups is tested using a Kaplan–Meier estimator of the cumulative distribution function at Day 180, with the rates being 19.8% and 33%, respectively, simulations (with sample size of 436 subjects) have shown that the power of detecting treatment difference is 0.811.

### 9.2.1. Interim Analysis 1

The first interim analysis for futility only will be performed when 112 subjects (25.7% of the planned 436 subjects) have completed the Day 28 visit or withdrew early from the study. No alpha will be spent during the first interim analysis. The stopping rule is nonbinding. When the conditional power is <20%, the sponsor may consider terminating the study if the totality of evidence is warranted. The conditional power is calculated assuming that the estimated treatment effect at the interim analysis is the true effect using the following formula (Jennison and Turnbull 2000):

$$\Phi\left(\frac{z}{\sqrt{t(1-t)}} - \frac{z_{\alpha/2}}{\sqrt{1-t}}\right)$$

where  $\Phi$  is the cumulative distribution function of the observed normalized test statistic  $z$ , and  $t$  is the information fraction (ie, observed sample at interim divided by total sample, which is the planned total sample size 436);  $t = 0.257$  at interim 1 and  $z_{\alpha/2} = 1.96$ .

### 9.2.2. Interim Analysis 2

The second interim analysis for both futility and efficacy will be performed when 240 subjects (55% of the targeted 436 subjects) have completed the Day 180 visit or withdrew early from the study.

The Hwang-Shih-DeCani alpha spending function with shape parameter -4 (O'Brien-Fleming like boundary) will be used to define the upper efficacy boundary for the primary analysis of ORR at Day 28 when approximately 240 subjects reach Day 180 (Hwang et al 1990). Based on enrollment projection, there will be approximately 360 subjects who have completed Day 28.

Table 8 lists the efficacy boundary when information fraction (ie, the percentage of subjects) is 0.826 (360 subjects complete Day 28) at interim 2; if ORR tested at Day 28 crosses the boundary, the key secondary endpoint, 6-month NRM, will be tested by passing the allocated alpha in this interim analysis to NRM. By simulation, without considering early stopping for futility, the power of testing 6-month NRM at Interim 2 (with 240 subjects complete Day 180) is about 0.608.

As in interim 1, conditional power based on test statistic of ORR at Day 28 will be recalculated using its observed information fraction and observed normalized test statistic at interim 2. The sponsor will consider stopping the study for futility if the conditional power is less than 20%. If neither the efficacy nor the futility boundary for testing ORR at Day 28 is crossed, the study will continue.

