3.3. Sample Size Considerations

A sample size of 414 subjects with 1:1 randomization (itacitinib vs placebo) and stratification based on baseline aGVHD risk status (standard risk vs high risk) provides approximately 90% power to test for the primary endpoint (ORR at Day 28) and approximately 80% power to test for the key secondary endpoint (NRM rate at Month 6). The family-wise α -level will be controlled at 0.025 overall for the two comparisons. Specifically, this study will claim to have achieved the efficacy objective when the primary endpoint ORR at Day 28 shows a significant treatment effect at 1-sided $\alpha = 0.025$. Conditional on significance of the primary endpoint, the key secondary endpoint (NRM rate at Month 6) will be tested at 1-sided $\alpha = 0.025$.

An absolute improvement of 16% in the primary endpoint of ORR at Day 28 would be considered a clinically meaningful improvement over standard first-line systemic treatment for aGVHD. A sample size of 414 subjects (207 subjects per treatment group) will provide approximately 90% power to detect a 16% overall difference (72% vs 56%) between treatment groups for the primary endpoint (ORR at Day 28) at a 1-sided alpha level of 0.025.

The assumed Day 28 ORR of 56% is based on MacMillan et al (2015). The stratum-specific response rates (standard risk, 68%; high risk, 44%) assume a standard risk:high risk ratio of 0.50:0.50. It is expected that treatment with itacitinib will result in a 16% increase in the ORR, that is, an expected odds ratio of 2.02 (which corresponds to an overall increase in ORR to 72%), with stratum-specific response rates of 81% and 61% for standard-risk and high-risk aGVHD cohorts, respectively. Power for the CMH test with stratification based on GVHD risk score was calculated using software N-Query 5.0.

[figure not shown]

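### The treated-arm stratum rates behind the power calculations average about 71% ORR and 20.3% NRM, not the stated 72% and 19.8%, so the quoted powers belong to slightly smaller effects than those they are paired with.

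*Protocol*

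**What the plan says.** Protocol 9.2 sets the primary comparison "for the primary endpoint (ORR at Day 28) at a 1-sided alpha level of 0.025", and adds: "A CMH test with 2-strata will be used". It states: "A sample size of 414 subjects (207 subjects per treatment arm) will provide approximately 90% power to detect a 16% overall difference (72% vs 56" per cent).

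On the control side, "The stratum-specific response rates (standard risk, 68%; high risk, 44" per cent) "assume a standard risk:high risk ratio of 0.50:0.50". For itacitinib it gives an odds ratio of 2.02, an overall ORR of 72%, and the strata "with stratum-specific response rates of 81% and 61" per cent. SAP 3.3 repeats these figures and ties the odds ratio to the overall rate: "which corresponds to an overall increase in ORR to 72" per cent.

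For NRM at Month 6, Protocol 9.2 assumes control rates of 22% and 44% (33% overall) and an itacitinib rate of 19.8% overall. That is 13.2 points, a 40% relative reduction, with odds ratio 0.50 and power 83%. It then says: "Stratum-specific NRM rates of 12.4% and 28.2% are expected for standard-risk and high-risk cohorts". SAP 3.3 carries the same NRM rates but quotes a power of approximately 80%, obtained by simulation. The Synopsis repeats the 16-point and 13.2-point differences with the 90% and 83% powers.

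**The concern.** The control strata average exactly to their stated overall rates. The treated strata do not, for either endpoint. The sentences that define the design alternative for the primary and key secondary endpoints therefore contain two different alternatives, and it is unclear which one each power describes. Anyone re-deriving the sample size will meet the mismatch. The Protocol also quotes a Kaplan-Meier simulation power of 0.811 at 19.8% versus 33% beside the CMH power of 83%, and a reader would take the two as describing the same effect.

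**Working it through.** **Inputs (Protocol 9.2).** 207 per arm, two equal strata, 1-sided 0.025. Control ORR 68% and 44%; treated 81% and 61%; odds ratio 2.02. Control NRM 22% and 44%; treated 12.4% and 28.2%; odds ratio 0.50.

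**Averages at 50:50**
- Control: (68 + 44)/2 = 56.0% and (22 + 44)/2 = 33.0%, as stated.
- Treated: (81 + 61)/2 = 71.0%, not 72%; (12.4 + 28.2)/2 = 20.3%, not 19.8%.

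**Could rounding explain it?** No. The largest ORR mean consistent with the printed rates is (81.5 + 61.5)/2 = 71.5%. The smallest NRM mean is (12.35 + 28.15)/2 = 20.25%.

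**Could another stratum mix explain it?** No.
- ORR of 72% needs a standard-risk share of (72 − 61)/(81 − 61) = 0.55, which moves control ORR to 0.55 × 68 + 0.45 × 44 = 57.2%.
- NRM of 19.8% needs (28.2 − 19.8)/(28.2 − 12.4) = 0.53, which moves control NRM to 32.3%.

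**Where the printed rates come from**
- Odds ratios of the overall rates: (0.72/0.28)/(0.56/0.44) = 2.020; (0.198/0.802)/(0.33/0.67) = 0.501. These match the stated 2.02 and 0.50.
- Applied within strata, with treated odds = OR × control odds: 2.02 × 2.125 = 4.2925, giving 81.1%; 2.02 × 0.7857 = 1.587, giving 61.3%. Likewise 0.50 × 0.2821 gives 12.4% and 0.50 × 0.7857 gives 28.2%. All four printed rates are reproduced.
- Unrounded means are 71.2% and 20.3%, so the differences are 15.2 and 12.7 points, the latter a 12.7/33 = 38.5% relative reduction. An odds ratio is not collapsible over strata: the overall value used inside strata yields a smaller overall effect.

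**Power of the two-stratum CMH test.** With m = 103.5 per arm per stratum and p̄ the mean of the two arms' rates in a stratum:
- D = Σ (m/2)|p_T − p_C|
- V0 = Σ m² p̄(1 − p̄)/(2m − 1)
- V1 = Σ (m/4)[p_C(1 − p_C) + p_T(1 − p_T)]
- Power = Φ[(D − c − 1.96√V0)/√V1], with c = 0.5 for continuity correction and 0 without.

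| Treated rates | D | √V0 | √V1 | Corrected | Uncorrected |
|---|---|---|---|---|---|
| ORR, OR 2.02 (mean 71.2%) | 15.759 | 4.778 | 4.702 | 0.895 | 0.913 |
| NRM, OR 0.50 (mean 20.3%) | 13.163 | 4.404 | 4.343 | 0.823 | 0.852 |
| ORR averaging 72% | 16.560 | 4.768 | 4.685 | 0.924 | 0.938 |
| NRM averaging 19.8% | 13.662 | 4.392 | 4.327 | 0.854 | 0.879 |

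The first two rows reproduce the Protocol's figures: the corrected values are close to the stated 90% and 83%. Simulation at the stratum rates (200,000 trials per scenario) gives 0.898 and 0.826 with the correction.

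The last two rows use the common within-stratum odds ratios that make the means come right: 2.10 (strata 81.7% and 62.3%) and 0.485 (strata 12.0% and 27.6%).

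**NRM at the SAP's level.** SAP 3.4.2 and 9.1.2 test NRM at 1-sided 0.0125. Replacing 1.96 by 2.241 in the last row gives (13.662 − 0.5 − 9.845)/4.327 = 0.77, power 0.78 corrected; and 3.817/4.327 = 0.88, power 0.81 uncorrected.

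**The case against.** The strongest reply is that this is a labelling slip of 0.8 and 0.5 points. The stated powers fit the stratum rates from which they were evidently computed, the direction is conservative, and no test, boundary or decision rule uses these rates. All of that stands.

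It can also be said that neither document explains how the stratum rates were derived. That is true: the use of the overall odds ratio within strata is an inference, although it reproduces every printed rate. The averaging mismatch does not depend on it.

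Four stronger readings are tempting, and the documents do not support them.
- A reader might infer that the powers of 90% and 83% were miscalculated. They were not, provided a continuity correction was used; the documents do not say. Without it the values at the stratum rates are 0.913 and 0.852.
- A reader might infer that the trial is too small. The effects actually powered are smaller than those stated, so 414 evaluable subjects give at least the stated power at 16 and 13.2 points under the Protocol's test and level.
- A reader might infer that NRM power is safely above 83%. That holds only at 1-sided 0.025. At 0.0125 it is about 0.78 to 0.81 on a single look. The SAP's NRM analysis also leaves out relapse deaths and early withdrawals (SAP 7.4.1), so fewer than 414 subjects may contribute.
- A reader might set these CMH powers against the SAP's approximately 80%. That figure is simulated, in a paragraph describing a Kaplan-Meier-based test, so the comparison says nothing about this error.

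**Conclusion.** The design alternative is internally inconsistent as written. At the stated equal mix, the treated strata imply an ORR of 71.0% (71.2% unrounded) and an NRM of 20.3%, against 72% and 19.8% stated. The quoted powers describe differences of 15.2 and 12.7 points, and the latter falls short of the 40% reduction declared clinically meaningful. At the stated overall effects, power at 1-sided 0.025 is about 2 to 4 points above 90% for ORR and about 2 to 5 points above 83% for NRM, depending on the continuity correction.

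This rests on 207 per arm, equal strata, a common odds ratio across strata and a single look at 1.96. It is a minor correction that leaves the sample size and the tests unchanged.

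**What to change.** Amend the Synopsis, Protocol 9.2 and SAP 3.3 in one of two ways.

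- (a) Keep 16 points and the 40% reduction as the clinically meaningful effects, but state that the 90% and 83% powers were computed at 71.2% versus 56% and 20.3% versus 33%. Keep the two ideas separate, so that the clinical threshold does not appear to have been lowered.
- (b) Keep 72% and 19.8%, and restate the stratum rates (81.7%/62.3% and 12.0%/27.6%), the within-stratum odds ratios (2.10 and 0.485) and the matching powers (0.924 and 0.854 corrected, or 0.938 and 0.879 uncorrected).

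In both cases, name the continuity-correction convention and state that the NRM powers apply at 1-sided 0.025, not at the SAP's Bonferroni 0.0125.

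The cost is a few sentences in two documents. Sample size, alpha, boundaries and analyses are unaffected.
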